3.7. Project/ research management

This section includes a discussion on

Ethical consideration (if applicable) (include confidential/ sensitive information or intellectual property information)	This study will be submitted for review to Taibah University College of Dentistry Research Ethics Committee (TUCDREC).
In the case of requesting a waiver of documentation of consent form; Please justify.	No waiving of documentation of informed consent form will be requested, a copy of the consent form is attached with this application
Potential Risk or problems & safety consideration	There is no risk to the patients and all collocated data will be anonymous.

Benefits of participating in the study	
All patients in both groups will be received non-surgical periodontal therapy that will improve their periodontal status.
 
The present study will support or contradict previous studies which have reported the relations between the periodontal therapy and the glycemic control.

Project plan (including other required administrative approvals, fieldwork information, facilities, timeframe, cost & budget justification, resources, health & safety considerations)	
The follow-up period in this study will be 3 months

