3.5. Theoretical framework and methods/approach

Methodology (The methodology, design, and materials, sample and sampling technique, description of study tools to be used).

A prospective, randomized controlled clinical trial will be conducted on two parallel groups with three months follow-up period. A convenient sample of 44 patients aged 40-70 will be recruited.

Test group (patients will give immediate periodontal therapy)

Control group (patients will give delayed periodontal therapy)

The subjects with uncontrolled type 2 diabetes (HbA1c from 7% to 9%) will be selected from attendants of Internal Medicine Outpatients Clinic, Tanta University Hospital and will be referred to Periodontology Department, Tanta University.

Closed envelopes technique will be used for random allocation of the study participants that identify to which group the subjects will be enrolled, using 1:1 allocation ratio. All patients will sign informed consent

Inclusion criteria

- Diagnosis of diabetes type 2 for more than five years
- Type 2 diabetes with HbA1c level from 7% to 9% at the last medical evaluation
- Age from 40 to 70 years
- No change of diabetes treatment over the previous three months
- Diagnosis with chronic periodontitis
- Minimum sixth permanent teeth excluding third molars
- Clinical attachment level (CAL) and pocket depth (PD) ≥ 4 mm in more than thirty percent of the sites

Exclusion criteria

- Pregnancy
- Alcoholism and smoking
- Presence of any systemic disorders other than hypertension and diabetes

- Diabetic major complications
- Antimicrobial therapies in the last 6 months
- Periodontal therapies in the last 6 months
- Allergy to metronidazole and amoxicillin

Intervention protocol

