Periodontal therapy will include scaling and root planing (SRP), combination of systemic antibiotics[metronidazole 400 mg three times daily for two weeks and amoxicillin 500mg three times daily for two weeks] and oral hygiene instructions (OHI). Full-mouth SRP will be performed by the same specialist for all patients in a test group using ultrasonic apparatus and Gracey curettes in a single two-hour session. Local anesthesia will be applied when needed. SRP will be associated with subgingival irrigation by chlorhexidine 0.12% mouthwash. Immediately, after SRP, the administration of antibiotics combination will be started and patients will receive a free dental care products necessary for periodontal maintenance during a follow-up period (three months). For the patients within a control group delayed periodontal therapy will be performed using the same procedures that will be applied for the patients in a test group exactly after the end of follow up period (three months) because of ethical reasons. Therefore, within the control group, no periodontal therapies will be done during the follow-up.

Clinical and metabolic follow-up

A complete medical history, socio-demographic data, and information regarding daily dental care will be collected for all patients. Charting for the full-mouth periodontium using a periodontal probe will be performed by the same specialist. This includes PD, CAL, bleeding on probing and the visible dental plaque. The periodontal evaluation will be done at baseline and at three months. Blood will take from a peripheral vein to monitor HbA1c using high-performance liquid chromatography at baseline and at three months post-treatment.

Data analysis (The proposed method of data analysis)

Data will be coded, collected and analyzed using the SPSS software under Mac OS Majave Version 10.14. Descriptive statistics will be done using mean and standard deviations, followed by inferential statistics using the Fisher's exact test, Chi-Square test, student t- test and paired t-test. Significance was adopted at $p<0.05$ which will be used as a cutoff point to control for alpha error.

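### The risk section states that there is no risk, yet all 44 patients are scheduled for two weeks of two systemic antibiotics and the visible text plans no systematic recording of adverse events

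*Combined protocol and SAP*

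**What the plan says.** The risk and safety field in Section 3.7 consists of one sentence: "There is no risk to the patients and all collocated data will be anonymous".

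Section 3.5 (intervention protocol) prescribes "metronidazole 400 mg three times daily for two weeks and amoxicillin 500mg three times daily for two weeks". This comes with a single two-hour full-mouth scaling and root planing (SRP) session, chlorhexidine irrigation, and local anaesthesia when needed. In the test group, "the administration of antibiotics combination will be started" immediately after SRP. Controls receive the same procedures "exactly after the end of follow up period (three months) because of ethical reasons". The benefits field in Section 3.7 confirms that both groups are treated.

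The exclusion criteria in Section 3.5 include "Allergy to metronidazole and amoxicillin".

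On follow-up, Section 3.5 says: "A complete medical history, socio-demographic data, and information regarding daily dental care will be collected for all patients", with no time attached. For the probing measures it says: "The periodontal evaluation will be done at baseline and at three months". Blood is taken "to monitor HbA1c using high-performance liquid chromatography at baseline and at three months post-treatment".

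The data analysis paragraph contains no safety item. The project-plan field in Section 3.7, whose label asks for health and safety considerations among other things, gives only the length of follow-up.

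**The concern.** Two things do not fit together. The risk field denies any risk, while the treatment includes two weeks of two systemic drugs for every patient. An exclusion for allergy to those drugs makes sense only if they can cause harm.

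The schedule adds to this. The visible plan describes no collection, reporting or analysis of adverse events, and its timed assessments miss the period when a drug reaction would be expected to appear.

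Patient safety and balanced reporting are at stake. Section 3.4 presents the antibiotic and antiseptic package as what sets this trial apart and regards SRP with oral hygiene instruction alone as less than optimal. A reader deciding whether the antibiotics are worth adding needs harms as well as benefits, and the visible plan provides systematically only for the benefits.

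**Working it through.** The plan gives no safety figure and no event rate, so there is nothing of its own to reproduce. The check covers exposure, timing and what could be learned.

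**Inputs from Section 3.5.** 44 patients; 1:1 allocation, taken as exactly 22 and 22; three doses a day of each drug for 14 days; test course starts right after SRP; control course starts after month three; timed assessments at baseline and three months.

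**Exposure**
- Courses: 22 (test, during follow-up) + 22 (control, after follow-up) = 44.
- Doses per drug per course: 3 × 14 = 42.

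**Gap from the end of the test-group course to the three-month assessment.** Three months is taken as 84 to 92 days. The HbA1c wording refers to time after treatment, and the treatment includes the antibiotics, so two starting points are possible.
- Counted from SRP: 84 − 14 = 70 days (10.0 weeks) to 92 − 14 = 78 days (11.1 weeks).
- Counted from the end of the antibiotics: 84 days (12.0 weeks) to 92 days (13.1 weeks).

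The range is therefore about 10 to 13 weeks. The control course begins after that assessment. On either count, no course has a timed assessment during it or in the weeks just after it.

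**Chance that there is something to record.** Let p be the probability that a course causes a reaction worth recording. The values of p are assumed. Expected events in the test group are 22p; the chance of at least one is 1 − (1 − p)^22.

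| Assumed p | Expected in 22 test courses | Chance of at least one in 22 |
|---|---|---|
| 1% | 0.22 | 20% |
| 5% | 1.1 | 68% |
| 10% | 2.2 | 90% |
| 20% | 4.4 | 99% |

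**What recording could show.** With 0 events in 22, the upper exact two-sided 95% limit is 1 − 0.025^(1/22) = 15.4%. Even a clean record would not establish that there is no risk.

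**The case against.** The plan has real safeguards. Pregnancy, major diabetic complications, other systemic disorders and drug allergy are exclusions, and an ethics committee reviews the study. These stand, but they screen and oversee; they do not record events.

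A reader might infer that the trial will end with no drug-reaction data at all. The documents do not support that. They are silent on adverse events and do not say that none will be recorded. The medical history has no stated time, so a history at three months that brings out a reaction is not ruled out. What the text supports is that no systematic recording is planned in the visible pages.

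A reader might also infer that patients are told there is no risk. Section 3.7 says a consent form is attached to the application, but it is not in the text available here, and it may describe the risks or tell patients how to report problems.

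Two further points have some force. Only about 22 courses fall within the follow-up. The control courses are delayed care given for ethical reasons, so the lack of trial data on them is a weaker criticism. Extra contacts could also prompt self-care in controls or strengthen adherence in the test group, which matters because Section 3.4 wants controls to have no active therapy. This affects how contacts should be made but does not defend the risk statement.

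Finally, the allergy exclusion could be read as requiring allergy to both drugs. In a list of exclusions it is naturally read as allergy to either, and nothing here depends on it.

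**Conclusion.** The concern holds as a should-fix point. The no-risk statement is inconsistent with the treatment and the exclusion criteria in Section 3.5, and the visible text plans no systematic recording of adverse events for any of the 44 scheduled courses.

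Confidence is high on the textual mismatch. It is lower on the consequence, because events might be picked up informally and their rate is unknown: at the 1% end of the assumed range there would probably be nothing to record among the test patients, while at 5% or more there probably would be.

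A reader might take this as a threat to the main result. It is not: the randomised HbA1c comparison does not depend on adverse event recording and is not affected.

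**What to change.** 1. Replace the statement in Section 3.7 with the risks of the planned treatment, and check that the consent form agrees.
2. Record adverse events on one standard form, asked the same way in both groups, at a brief contact at about week 2 and at the three-month visit. The week-2 contact should follow a fixed script and give no oral hygiene advice, so that the control condition is kept.
3. Report events by group as description only, without a test.
4. Ask controls once near the end of their delayed course, and report those events separately without comparison.

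**Cost.** A short amendment, a consent change only if the form repeats the no-risk statement, one form page, and 22 (test, week 2) + 22 (control, week 2) + 22 (control, delayed course) = 66 brief contacts. For controls, recording runs about two weeks past month three. There is a small chance that contact changes behaviour or adherence. The data will be imprecise, as the 15% limit for 0 of 22 shows, so they can describe tolerability but not establish safety.
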